- 4. evaluate the effect of the intervention program on other delay time intervals, including, symptom onset to contact with emergency medical personnel (either EMS or acute ED), symptom onset to receipt of reperfusion treatment in patients receiving such treatment, and symptom onset to time of taking action.

- 5. evaluate the effect of the intervention program on medical care and health outcomes in patients with diagnosed acute cardiac ischemia, including receipt of thrombolytic therapy and other reperfusion therapy, AMI severity, in-hospital case fatality rates, length of hospital stay, and community-wide CHD mortality rates.
- 6. evaluate the effect of the intervention program on utilization of medical services, including 911/EMS and E.D. and hospital admissions.
- 7. evaluate the impact of the intervention program on delay time in subgroups by gender, age, and race/ethnicity.

REACT will also:

- 1. estimate the current national average delay time and its trends from onset of AMI symptoms to ED arrival, and to describe the distribution of delay times by race/ethnicity, gender, age, socioeconomic status, geography, and symptom pattern.
- 2. study differences among communities and among subgroups identified by race/ethnicity, gender, and age, in symptom presentation and outcomes of acute ischemic cardiac disease.
- 3. study hospital practices for thrombolytic and other reperfusion therapy, and describe the distribution of such treatment by patient race/ethnicity, gender, age, and socioeconomic status.
- 4. evaluate, amongst patients receiving thrombolytic and other coronary reperfusion strategies, the time-to-treatment effect on in-hospital case fatality rates overall and by subgroups identified by race/ethnicity, gender, age, socioeconomic status, and geography, controlling for AMI severity.
- 5. contribute to methods for measuring and analyzing delay time and its components in diverse population groups with suspected acute cardiac ischemia.
- 6. study factors associated with various phases of the delay interval as well as overall delay time, including situational characteristics (e.g., location during symptoms, presence of others, day of week, etc.).
- 7. study patterns of behavior, including patient actions such as self-care, in response to AMI symptoms.
- 8. determine the impact of the various program components on knowledge, attitudes, skills, and behaviors of the general public and patients with acute CHD.

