This group of patients was chosen as the population for the primary analysis for several reasons. First, this group includes those patients who will benefit most from a reduction in delay time by virtue of faster receipt of medical services. Hence, the presence of a reduction in delay should be established in this group, rather than in the larger group of patients that also includes those who have non-cardiac causes of their symptoms. Second, patients with cardiac diagnoses will be more stable across communities and over time than the larger group of patients with symptoms suggestive of acute IHD. Third, patients with cardiac diagnoses will be identified more uniformly and consistently across Field Sites and over the study period. Fourth, sufficient numbers are expected for the purposes of statistical precision and power to adequately examine differences in the primary trial outcomes between intervention as compared to control communities.

A 30-40 minute net reduction in median delay time is considered to be a clinically meaningful intervention effect; thus, in the primary analysis, we will examine delay time as a continuous variable. However, it is also important to increase the percentage of patients who arrive at the hospital within six hours of onset of acute

symptoms, early enough to be treated within the optimal window for receipt of thrombolytic therapy or immediate PTCA. Thus, we will also examine delay time classified as a dichotomous variable (i.e. the proportion of cases delaying < six hours vs $\geq six$ hours).

G. Secondary Outcomes

The following secondary outcomes will be measured and analyzed. The definition and measurement of each outcome is described in Section VII.

- 1. Secondary Populations and Subgroups
- a. The primary intervention effect will be examined among *patients with* diagnosed MI. Since this subgroup includes the vast majority of patients eligible for thrombolytic therapy and/or immediate PTCA, we will examine the intervention effect on their prehospital time delays.
- b. The primary intervention effect will be examined in patients seen in the ED for chest pain and admitted for possible acute ischemia. These patients have been identified by physicians as warranting further diagnosis and/or treatment, and they are targets of the intervention.

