- c. The primary intervention effect will be examined in patients seen in the ED for chest pain/discomfort and sent home. Since the intervention messages focus on chest pain, these patients are also targets of the intervention.
- d. The primary intervention effect will also be examined in subgroups defined by factors associated with delay that might affect the effectiveness of the intervention. These are sex, race/ethnicity, age, history of previous CHD, health insurance coverage, and current event (AMI vs. unstable angina vs. other cardiac diagnoses).
- 2. Secondary Definitions of Delay Time

Since the different components of the delay interval may be affected differentially by the intervention, alternative definitions of delay time will be examined. We hypothesize that all delay times will be reduced by the intervention. The following definitions will be offered:

- a. Time from onset of acute symptoms to taking action to seek care (e.g., time of calling 911) because this reflects patient recognition and action.
- b. Time from onset of acute symptoms to in-person contact with the medical care system (either the ED or the EMS) because this reflects time to contact with any available treatment.
- c. Time from onset of symptoms to receipt of reperfusion therapy (thrombolytic therapy or immediate PTCA) among those who receive such therapy.
- 3. Secondary Outcomes

We will examine the effect of the intervention on the following outcomes:

a. Receipt of early revascularization in patients with IHD diagnosis (ICD 410/411): thrombolytic therapy or immediate PTCA.

Receipt of myocardial revascularization procedures, reperfusia or artery opening therapy is hypothesized to increase because earlier arrival will increase the proportion of patients who are eligible for treatment.

b. Severity of infarction (e.g., peak CPK, peak LDH) in patients with AMI diagnosis (ICD 410)

Severity of infarction is hypothesized to decrease because earlier treatment will reduce infarct size.

c. In-hospital case-fatality rates in patients with cardiac diagnoses.

Case fatality is hypothesized to decrease because earlier treatment will reduce infarct size and improve survival.

d. Duration of hospitalization in patients with cardiac diagnoses.

Duration of hospitalization will be reduced.

e. Total community CHD mortality.

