Two, somewhat different, types of messages will be used: 1) a simple message, emphasizing chest pain as the primary symptom and shortness of breath as a commonly occurring symptom, but ensuring that this message is framed to convey that chest pain and shortness of breath may not be the only symptoms which occur, for use with the large media portions of the community education component; and 2) a more complex message, emphasizing the variety of symptoms that may occur, for use with the interpersonal methods proposed for the patient component of the intervention and the group education sessions of the community education component. The action component of the message will to be to get to the ED quickly, preferably by calling 911.

We conceptualize two major groups of strategies of intervention delivery: interpersonal strategies and impersonal strategies. *Interpersonal strategies* are those which involve interaction between at least two people, such as individual counseling, group education or counseling, or telephone contact and education. *Impersonal strategies* are those which do not involve interpersonal interaction, such as various media approaches, using both large (TV, radio, newspapers) and small (pamphlets, posters, or videotapes) media. Within each intervention strategy, a variety of techniques or methods could be used, such as role modeling with or without role play, and contracting. Objectives for each intervention component have been designed to affect: 1) awareness and knowledge; 2) attitudes and beliefs; and 3) skills or capabilities.

B. Theoretical Model

In considering the theoretical model for the proposed intervention, we addressed two different forms of theory: behavior change theory and implementation theory. While elements of other theories were considered, two theories served as the primary behavior change theoretical basis upon which the four components of our proposed intervention have been developed: Social Cognitive Theory and Self-Regulatory Theory. These behavior change theoretical approaches are described below along with the overall, combined study approach. We also considered the theoretical

methods that would be used for implementing the interventions. Three primary theoretical approaches emerged: Diffusion Theory, Social Marketing Theory, and Community Organization Theory.

1. Behavior Change Theories

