For those patients transported by EMS personnel, the interval defined as the time from symptom onset until EMS personnel arrival at patient location will also be measured (note: if arrival time to patient is not available, arrival at geographic location will be used). EMS records (appended to the patient medical record or obtained from EMS agencies) will be reviewed to determine the time of EMS arrival. Because EMS unit staffing and equipment may vary, as may availability of a tiered EMS response, the times of first arrival will be collected separately for the first basic emergency medical technician (EMT), the first defibrillator equipped and trained person (e.g., EMT-D or paramedic), and the first paramedic. These additional time endpoints will be used in subgroup analyses (see below).

c. Interval from symptom onset until initiation of reperfusion therapy

In the eligible population of patients with AMI, the time reperfusion therapy (i.e., coronary angioplasty, thrombolytic agents, or coronary artery bypass surgery) is initiated will be determined by chart review. Subgroup analyses will individually address each specific type of reperfusion therapy.

3. Secondary Outcomes

a. Receipt of early revascularization or reperfusion therapy: thrombolytic therapy, immediate PTCA, or either.

Hospital records will be reviewed to determine the receipt and timing of such therapy. Based on NHAAP guidelines, therapy within one hour of ED arrival will be considered "early."

b. Size of MI and severity of infarction

The size of MI will be estimated by use of peak cardiac enzyme levels. While standardized assays will not be available at all trial hospitals, it is expected that each institution will demonstrate satisfactory consistency of test use and standards. Data will be obtained regarding the type of test, time of peak level draw, and peak value for each enzyme ordered. The upper limit of normal will be obtained from the hospital lab on a regular basis.

Severity of infarction will be assessed by hemodynamic instability and the occurrence of ventricular arrhythmias. Hemodynamic instability will be measured by vital signs at presentation, i.e. initial heart rate and initial blood pressure upon hospital presentation.

c. In-hospital case fatality

Hospital discharge status (dead or alive) will be obtained from medical records for the primary population.

d. Length of stay (LOS)

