The effect of intervention on reducing delay time will be declared significant if the two-tailed significance of the τ_k term is less than 0.05. This model is comprehensive enough to include the most important factors related to delay time, without being overly complicated.

- b. A simpler two stage procedure will be performed in which the model in the first stage will be identical to (1), except there will be no adjustment for covariates. That is, the term $\mathbf{q}^T(\mathbf{x} \overline{\mathbf{x}})$ will be dropped from (1). Other than this change the analysis will be conducted exactly as in the primary analysis.
- c. A further analysis will dichotomize delay time into \leq six hr. vs. \geq six hours. The result will be correlated binary data because some patients may have more than one observation. The Generalized Estimating Equation (GEE) approach (105) with an exchangeable working correlation matrix will be used to model the logit of p = the probability of arriving within 4 hours:

$$\ln\left(\frac{p}{1-p}\right) = \mu_i + \theta^T (\mathbf{x} - \overline{\mathbf{x}}) + \beta_i t + \varepsilon_{ijk}$$
(4)

The terms on the right side of (4) are as defined after (1), and ln denotes the natural logarithm. The estimates, b_i , of the slopes β_i , will be computed in each community. The 10 intervention slopes will be compared to those of the matching control communities using a two-tailed, paired t-test at α =0.05.

3. Secondary definitions of delay time

The same analysis as for the primary endpoint will be conducted in a random sample of the primary population, using data collected by telephone interview and record abstraction, for alternative definitions of delay time, as follows.

- a. Time from onset of symptoms to when emergency care is sought. Because this could be 0, log(delay+.1 hr) will be used in the analysis.
- b. Time from onset of symptoms to treatment by emergency personnel (including ambulance personnel).
- c. Time from onset of symptoms to "definitive treatment" among those who receive definitive treatment.
- 4. Analysis of delay time in secondary populations

The intervention effect on delay time will be assessed in a random sample of patients presenting at the ED with chest pain, but not admitted to the hospital. The same primary analysis that was used for the primary population will be used for this population.

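### The secondary time-to-medical-contact interval has three incompatible definitions, and the Section VII version would compare arms within EMS-transported patients only

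*Protocol*

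**What the plan says.** - **I.B, secondary aim 4** names the interval as "symptom onset to contact with emergency medical personnel (either EMS or acute ED".
- **IV.G.2.b** repeats it: "Time from onset of acute symptoms to in-person contact with the medical care system (either the ED or the EMS". IV.G.2 adds the hypothesis that the intervention will reduce all delay times. IV.G opens with a pointer: "The definition and measurement of each outcome is described in Section VII".
- **VII.A.2.b**, where that pointer leads, has a heading that names EMS personnel only. Its text begins "For those patients transported by EMS personnel, the interval defined as the time from symptom onset until EMS personnel arrival" and ends the interval when EMS reaches the patient. It says this interval will *also* be measured, from EMS records attached to the chart or obtained from EMS agencies.
- **XI.B.3.b** lists "Time from onset of symptoms to treatment by emergency personnel (including ambulance personnel". The opening sentence of XI.B.3 puts all the alternative delay definitions in one analysis, "conducted in a random sample of the primary population, using data collected by telephone interview and record abstraction".

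Four other statements bear on the point. The action message in V.A is to "get to the ED quickly, preferably by calling 911". I.D and IV.G.3 expect EMS use to rise. II.D.3 reports shorter delays in patients brought by EMS than in those who come by car. V.E.2.c says that only a minority of MI patients use EMS.

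**The concern.** The three versions would give three different results. The first includes everyone and stops at the first professional contact by either route. The second drops everyone who came by car. The third waits for treatment, which is a later event than contact.

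The second version carries an extra hazard. Arrival by EMS is a behaviour after randomization, and the intervention promotes it. If more people in intervention communities call 911, the EMS group there takes in people who would otherwise have travelled by car. By the protocol's own review of the literature, those people have a different delay distribution. The EMS-only mean can then move because the group's membership changed, even if no individual reached contact sooner. Such a comparison cannot cleanly test the IV.G.2 hypothesis that all delay times fall.

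**Working it through.** **1. The definitions side by side**

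| Place | End event | Patients |
|---|---|---|
| I.B aim 4; IV.G.2.b | first in-person contact, EMS or ED | every eligible patient |
| VII.A.2.b | EMS arrival at the patient | EMS-transported only |
| XI.B.3.b | treatment by emergency personnel | random sample of primary population |

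No two rows agree on both columns. Section VII never constructs the EMS-or-ED interval, although VII.A.1 has ED arrival time recorded, so the times needed for it are collected.

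**2. The random sample**

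In VII.A.2.a random sampling belongs to the telephone interview, which supplies the time of taking action. VII.A.2.b takes EMS arrival from records and mentions no sampling. XI.B.3 extends the sample to all the alternative definitions and gives no sample size.

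**3. The plan's detectable effects, reproduced**

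Inputs from Section X and Appendix C: σ = log10(9)/2 = 0.477, V_t = 0.237 yr², J = 10, L = 1.5 yr, t with 9 df (2.262 + 0.883 = 3.146), equal K per community.

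SE²(d̄) = 2σ_β²(1−ρ)/J + 2σ²/(K·V_t·J), with σ_β = log10(R_β)/(2L). Relative reduction = 1 − 10^(−L·3.146·SE).

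- K = 600, best case (R_β = 1.05, ρ = 0.4): SE² = 0.0000060 + 0.000320 = 0.000326, giving 17.8%. Worst case (R_β = 1.15, ρ = 0): 19.6%. Table 9 prints 18% and 20%.
- 40% subset (K = 240): 26.5% and 27.6%. Table 9 prints 27% and 28%.
- 30% subset (K = 180): 29.9% and 30.8%. Table 9 prints 30% and 31%.

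The formulas reproduce the table. For an EMS-only analysis the relevant rows are the subset rows. The 30-40% share is my assumption, since the protocol says only that EMS users are a minority.

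**4. Illustration of the selection effect**

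Assume no patient's time to contact changes. Let p be the baseline EMS share, s the net rise in intervention communities by the end of the trial, and R the ratio of switchers' times to those of existing EMS users. The protocol gives none of these. Then:

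apparent ratio of EMS-only geometric means = R^(s/(p+s))

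- p = 0.49, s = 0.05, R = 1.25: 1.25^0.0926 = 1.021, or +2.1%.
- p = 0.40, s = 0.10, R = 1.5: 1.5^0.20 = 1.084, or +8.4%.
- p = 0.30, s = 0.15, R = 2.0: 2.0^0.333 = 1.260, or +26.0%.

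These are the smallest, a middle and the largest value over p = 0.30 to 0.49, s = 0.05 to 0.15 and R = 1.25 to 2.0.

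On the log scale used in the analysis, the largest shift is ln 1.26 = 0.231. The 30-31% detectable in a 30% subset is 0.357 to 0.371, so the shift is about 62-65% of it. The middle case (0.081) is about a quarter of the 27-28% detectable in a 40% subset (0.315 to 0.329).

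Every R above is greater than 1, so every shift is a lengthening that would mask benefit. If switchers had shorter times than existing EMS users, the sign would reverse.

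**5. After the fix**

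With first contact by either route in every case, the analysed set no longer depends on transport, and the term R^(s/(p+s)) drops out. The full K = 600 then applies: 17.8% to 19.6% detectable, if this interval has the same residual variance as onset to ED arrival.

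**The case against.** The strongest defence is that VII.A.2.b only supplies the EMS half of the IV.G.2.b interval. It says *also* measured, ED arrival is recorded for patients generally, and XI.B.3 draws on the primary population rather than on EMS users. XI.B.3.b refers to emergency personnel *including* ambulance staff, which implies that ED staff count too. On that reading nobody would compare arms within EMS users.

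This stands as far as it goes. A reader might infer that the planned comparison is selection-biased. The documents do not support that, because nowhere do they commit to an EMS-only comparison between arms. Four further inferences also fail:

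- **That the shift matches the 18-20% the trial can detect.** That figure is for the full K = 600. An EMS-only analysis has the larger detectable effects of the subset rows.
- **That the EMS-only interval could shorten with no change in behaviour.** If nobody changes behaviour, nobody switches to 911 and this mechanism does not operate.
- **That the analysis would use 200 cases per community.** That number belongs to the telephone interview (VII.C.3.a). XI.B.3 states no size.
- **That II.D.3 fixes the size of R.** It gives a direction without a magnitude, and it concerns delay in general rather than onset to EMS arrival.

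The defence does not remove the contradiction. IV.G names Section VII as the place where each outcome is defined, and an analyst who follows it finds only the EMS-transported version. Nor does the defence explain why XI.B.3.b ends at treatment when IV.G.2.b ends at contact.

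**Conclusion.** The contradiction is certain and can be read directly from the text: three end events and three populations for one secondary interval. The bias is conditional. It arises only if the interval is analysed as VII.A.2.b defines it, and its size and direction depend on EMS shares and switchers' times that the protocol does not give. Under the assumed ranges the EMS-only geometric mean would rise by about 2% to 26% with nobody acting sooner. Even the largest of these is below the 27-31% reduction detectable in a 30-40% subset, but it could conceal a good part of a real benefit. The point concerns one secondary delay definition. The primary endpoint, onset to ED arrival, is unaffected. The text should be reconciled before analysis.

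**What to change.** 1. In VII.A.2.b and XI.B.3.b adopt the IV.G.2.b definition: onset to the earlier of EMS arrival at the patient and ED arrival, with ED arrival as the contact time for patients not brought by EMS.
2. Apply it to all abstracted primary-population cases. The case subsampling of X.A in the larger communities can stay as planned.
3. In XI.B.3.b replace *treatment by* with *in-person contact with*.
4. In XI.B.3 limit the interview random sample to the interview-based time to action.
5. Report the EMS-only interval descriptively, next to the proportion arriving by EMS in each arm.

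The cost is modest but not zero. The change is mainly one of wording, since ED arrival is already recorded and VII.A.2.b already plans to obtain EMS records. Some of those records may have to be retrieved from EMS agencies, possibly for more cases than a sample would require, and the protocol does not state that burden. The EMS-only interval would no longer be a tested endpoint.
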